Table 1 represents the mean comparison between Mindfulness group and the Control Group of respondents while before and after intervention. On The Hamilton Anxiety scale, most of the respondents in The Mindfulness Group had very severe condition while before intervention with mean score (M=32.86), but it reduced to mean score (M=19.62). While in the control group, most of the respondents had very severe condition while before intervention with mean score (M=33.70) and moderate to severe condition while after intervention with mean score (M=28.00). The obtained t-value and p-value for Hamilton scale are 8.350 and 0.000 respectively. Here, p-value is less than 0.01; it indicates that there is a statistically significant difference between mindfulness and control group of respondents based on Hamilton scale. Similarly when considered the Subjective Unites of Dysfunction Scale (SUDS), most of the respondents of The Mindfulness Group, felt 'Freaking out' while before intervention with mean score (M=8.24) and 'Moderately upset' while after

intervention with mean score (M=5.69). But in the control group, most of the respondents felt 'Freaking out' while before intervention with mean score (M=8.27) and 'bad' while after intervention with mean score (M=6.03). The obtained t-value and p-value for SUDS are 1.228 and 0.225 respectively. Here, p-value is greater than 0.05, and indicated that there is no significant difference between mindfulness and control group of respondents based on SUDS. Similarly, obtained t-value and p-value for Quality of life are -2.229 and 0.030. Here p-value is less than 0.05; and shows a statistically significant difference between Mindfulness and Control group in relation to WHO Quality of life (QOL - BREF) scale of respondents.

	CBT (n=106)		Control (n=125)				
Scale	Pre	Post	Pre	Post	t-	F-	p-
	Mean±SD		Mean±SD		value	value	value
HAMA	32.52±5.24	21.03±4.29	33.70±6.08	28.00±6.49	6.905	2.312	0.000
SUDS	8.24±0.98	5.34±1.14	8.27±1.11	6.03±1.29	2.366	0.344	0.021
QOL	73.62±5.23	83.28±5.06	75.47±5.44	82.53±4.85	-2.714	0.002	0.009

Table 1: Mean comparison between CBT group (n=106) and Control group (n=125)

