Table 2 presents the mean comparison between CBT group and control group of respondents before and after intervention. On the Hamilton Anxiety scale, most of the respondents of the CBT Group had very severe condition while before intervention with mean score (M=32.52), which reduced to mild to moderate severe after the intervention witj mean score (M=21.03). In control group, most of the respondents were in very severe condition while before intervention with mean score (M=33.70) and improved to moderate to severe condition after the intervention with mean (M=28.00). The obtained t-value and p-value for Hamilton scale are 6.905 and 0.000 respectively. Here, p-value is less than 0.01, it indicates a statistically significant difference between CBT and control group of respondents based on Hamilton Anxiety scale. Similarly, on the SUDS of respondents, most of the respondents felt 'Freaking out' while before intervention with mean (M=8.24) and

'Moderately upset' after the intervention with mean (M=5.34). But in the control group, most of the respondents felt 'Freaking out' before the intervention with mean (M=8.27) and felt 'bad' after intervention with mean (M=6.03). The obtained t-value and p-value for SUDS is 2.366 and 0.021 respectively. Here, p-value is less than 0.05, indicating a statistically significant difference between CBT and control group of respondents based on SUDS. Similarly obtained t-value and p-value for Quality of life are -2.714 and 0.009. Here p-value is less than 0.01; indicating a statistically significant difference between CBT and Control group in relation to The WHO Quality of life (QOL- BREF) scale of respondents.

	Novel IVRTS (n=115)		Control (n=125)		t-	F-	
Scale	Pre	Post	Pre	Post	_		p- value
	Mean±SD		Mean±SD		value	value	value
HAMA	28.60±8.45	11.10±4.03	33.70 ± 6.08	28.00±6.49	8.088	23.503	0.000
SUDS	8.10±1.56	3.73 ± 1.23	8.27±1.11	6.03 ± 1.29	7.503	2.315	0.000
QOL	72.87±6.21	87.07±3.79	75.47±5.44	82.53±4.85	-6.313	4.519	0.000

Table 3: Mean comparison between IVRTS (n=115) and Control group (n=125)

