Table 3 presents the mean comparison between The Novel Intelligent Virtual Reality Therapy System (IVRTS) and control group of respondents. On the Hamilton Anxiety scale of, most of the respondents of the Novel IVRTS Group had a score representing moderate to severe condition before the intervention with mean (M=28.60), and reduced to mild condition after the intervention with mean (M=11.10). In the control group, most of the respondents were in very severe condition before intervention with mean (M=33.70) and moved to moderate to severe condition after intervention with mean (M=28.00). The obtained t-value and p-value for Hamilton Anxiety scale is 8.088 and 0.000 respectively. Here, p-value is less than 0.01, it indicates that there is a statistically significant difference between The Novel IVRTS Group and The Control Group on Hamilton scale. Similarly, on the SUDS of respondents, most of the respondents of The IVRTS Group felt 'Freaking out' before the intervention (M=8.10) and 'No Significant Distress' after the intervention with mean

(M=3.73). In the control group, most of the respondents felt 'Freaking out' before the intervention with mean (M=8.27) and moved to feeling 'bad' after the intervention with mean with mean (M=6.03). The obtained t-value and p-value for SUDS are 7.503 and 0.000 respectively. Here, p-value is less than 0.01, it indicates that there is a statistically significant difference between The Novel IVRTS Group and The Control group based on SUDS. Similarly, the obtained t-value and p-value for The WHO Quality of life Scale were -6.313 and 0.009. Here p-value is less than 0.01, and indicates a statistically significant difference between The Novel IVRTS and Control group on The WHO Quality of life (QOL-BRF) scale of respondents.

Scale	Mindfulness		CBT		Novel IVRTS		
	Pre	Post	Pre Post		Pre	Post	
	Mean±SD		Mean±SD		Mean±SD		
HAMA	32.86±5.76	19.62±4.24	32.52±5.24	21.03±4.29	28.60±8.45	11.10 ± 4.03	
SUDS	8.24 ± 0.95	5.69 ± 1.04	8.24 ± 0.98	5.34 ± 1.14	8.10 ± 1.56	3.73 ± 1.23	
QOL	73.86±7.73	84.10±5.19	73.62±5.23	83.28±5.06	72.87±6.21	87.07±3.79	

Table 4: Efficacy of Interventions based on the HAMA, SUDS and WHO QOL scale

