Finally Table 4, shows the comparison analysis between the various interventions to show which intervention proved to be the most effective and efficient for the patients. Interventions namely, Mindfulness Meditation, CBT and Novel Intelligent Virtual Reality Therapy System (IVRTS). The mean scores after intervention on both The Hamilton Anxiety Scale and The Subjective Units of Dysfunction Scale for the Novel IVRTS Group is significantly less than the mean scores (HAMA=11.10, SUDS=3.73) of The Mindfulness Group (HAMA=19.62, SUDS=5.69) and the CBT Group (HAMA=21.03, SUDS=5.34). In addition, The Novel IVRTS Group has a higher mean score on The WHO Quality of Life Scale (QOL=87.07) compared to the Mindfulness Group (QOL=84.10) and the CBT Group (QOL=83.28). The p-value is less than 0.01 respectively indicating a significant difference between Novel IVRTS compared to other interventions including CBT, Mindfulness and

Control groups. Considering the all the above comparisons of statistical significance modalities namely, The Mean Scores, Standard Deviations, t-scores and p-scores. The study concludes that, The Novel Intelligent Virtual Reality Therapy System (IVRTS) intervention is the most effective and efficient intervention compared to Mindfulness and even CBT.

Through the various approaches explained henceforth, the researchers aspired to create a more effective, image-based treatment system for phobias, based on the combination of principles of Psychology and Virtual Reality. The treatment methodologies thus aimed to automate the process oftherapy thereby making the process faster and more practical.

Moreover, the new technology is for the first time used to develop human, AI interaction for treatment, using interactive sensors, intelligent automated psychotherapy interface, and VR imagery scenarios.

DISCUSSION AND CONCLUSION

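### The claim that IVRTS is the most effective arm rests partly on t, p and SD values from tests against Control, which cannot rank the arms; no direct comparison with CBT or Mindfulness is reported

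*Combined protocol and SAP*

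**What the plan says.** The section OUTCOMES AND RESULTS names independent-sample t-tests and ANOVA as its between-group methods. It does not say whether the t-tests use post scores or change scores.

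Three tables each compare one active arm with Control: Mindfulness (Table 1), CBT (also captioned Table 1, discussed as Table 2) and IVRTS (Table 3). For HAM-A the text reports:

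- Mindfulness: "The obtained t-value and p-value for Hamilton scale are 8.350 and 0.000 respectively"
- CBT: "The obtained t-value and p-value for Hamilton scale are 6.905 and 0.000 respectively"
- IVRTS: "The obtained t-value and p-value for Hamilton Anxiety scale is 8.088 and 0.000 respectively"

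Table 4 sets the three active arms side by side with pre and post means and SDs, and no t, F, df or p. The text on Table 4 compares post means and then states "The p-value is less than 0.01 respectively indicating a significant difference between Novel IVRTS compared to other interventions including CBT, Mindfulness and" the Control group. It closes with "Considering the all the above comparisons of statistical significance modalities namely, The Mean Scores, Standard Deviations, t-scores and p-scores" and concludes that the IVRTS "intervention is the most effective and efficient intervention compared to Mindfulness and even CBT". DISCUSSION AND CONCLUSION and the ABSTRACT repeat the claim of superiority over CBT and Mindfulness.

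**The concern.** A t statistic is a difference divided by its standard error, and p is a function of t and the degrees of freedom. Computed against Control, both measure the evidence that an arm differs from Control. They depend on spread and sample size as well as on effect, so their order need not be the order of the effects. An SD describes spread and ranks nothing. Three of the four listed grounds therefore cannot carry a statement about which active arm works best.

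The fourth ground, the means, can describe an ordering. As printed it has no estimated difference between active arms, no confidence interval and no adjustment for the lower HAM-A baseline in the IVRTS arm (28.60, against 32.86, 32.52 and 33.70).

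What is at stake is the headline claim, which is also hypothesis (i). A reader cannot see how large the IVRTS advantage over CBT or Mindfulness is, how uncertain it is, or how much of it was present at baseline.

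**Working it through.** **1. What the printed statistics order.** Values are |t| and p against Control, from the three Control-comparison tables.

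| Scale | Mindfulness | CBT | IVRTS | Largest t |
|---|---|---|---|---|
| HAM-A | 8.350, 0.000 | 6.905, 0.000 | 8.088, 0.000 | Mindfulness |
| SUDS | 1.228, 0.225 | 2.366, 0.021 | 7.503, 0.000 | IVRTS |
| QOL | 2.229, 0.030 | 2.714, 0.009 | 6.313, 0.000 | IVRTS |

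The text on Table 3 gives the IVRTS QOL p as 0.009, where the table has 0.000.

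**2. What the means order.** HAM-A falls are:

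- IVRTS: 28.60 - 11.10 = 17.50
- Mindfulness: 32.86 - 19.62 = 13.24
- CBT: 32.52 - 21.03 = 11.49
- Control: 33.70 - 28.00 = 5.70

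Net of Control these are 11.80, 7.54 and 5.79. The means put IVRTS first, while the printed HAM-A t does not.

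**3. Size of the contrast being claimed.** The ANCOVA difference is the post difference minus b times the baseline difference, where b is the common slope on baseline. The documents give no b. Assuming it lies between 0 and 1, the HAM-A advantage of IVRTS is:

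- versus Mindfulness: post 19.62 - 11.10 = 8.52; baseline 32.86 - 28.60 = 4.26; adjusted range 8.52 (b = 0) to 4.26 (b = 1)
- versus CBT: post 21.03 - 11.10 = 9.93; baseline 32.52 - 28.60 = 3.92; adjusted range 9.93 to 6.01

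Up to half of the post-score gap from Mindfulness could thus reflect the baseline gap. The direction still favours IVRTS.

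**4. Can the printed HAM-A t-values be reproduced?** Inputs are the printed means, SDs and n (118, 106 and 115, against 125).

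*As post-score tests:* t = difference / [s_p × sqrt(1/n1 + 1/n2)], with s_p the pooled SD.

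- Mindfulness: 8.38 / (5.51 × 0.128) = 11.84; printed 8.350
- CBT: 6.97 / (5.59 × 0.132) = 9.44; printed 6.905
- IVRTS: 16.90 / (5.45 × 0.129) = 23.99; printed 8.088

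None matches, and the recomputed order puts IVRTS first.

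*As change-score tests:* SD of change = sqrt(s_pre² + s_post² - 2·r·s_pre·s_post), with the same assumed r in both arms.

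- Mindfulness: r = 0 gives t = 7.26; the printed 8.350 needs r of about 0.25
- CBT: r = 0 gives t = 5.49; the printed 6.905 needs r of about 0.37
- IVRTS: r = 0 gives t = 10.01 and r = 0.9 gives 22.27; the printed 8.088 needs r of about -0.60

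Across the nine t-values, six need a negative r.

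**5. Degrees of freedom implied by the printed t and p (two-sided, p to three decimals).**

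- 1.228 with 0.225: 48 to 56
- 2.229 with 0.030: 49 to 61
- 2.366 with 0.021: 56 to 76
- 2.714 with 0.009: 44 to 65

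All four fit about 57 df to within 0.001. The printed n give 118 + 125 - 2 = 241 for Mindfulness and 106 + 125 - 2 = 229 for CBT.

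**The case against.** The strongest defence is that the sentence lists four things together and never says that arms are ordered by t. Means come first in the list, the sentences just before it compare post means, and these favour IVRTS on HAM-A, SUDS and QOL. The t-values favour IVRTS on two of the three scales. On HAM-A the p-values are tied, not reversed. Direct post-score tests computed from the Table 4 means and SDs with the printed n would also favour IVRTS strongly: on HAM-A, t is 15.71 against Mindfulness and 17.74 against CBT, unadjusted for baseline.

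All of that stands, and it limits the point. It does not make t, p or SD valid grounds for ranking, and it does not supply the missing tests behind the asserted p.

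Three stronger readings are tempting and are not supported:

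- *That the stated basis contradicts the conclusion, or that Mindfulness is really best.* A smaller t is not a smaller effect, and the HAM-A order reverses when t is recomputed from the printed post means, SDs and n.
- *That QOL is a second conflict.* On QOL, t and p place CBT above Mindfulness ("Similarly obtained t-value and p-value for Quality of life are -2.714 and 0.009" against "Similarly, obtained t-value and p-value for Quality of life are -2.229 and 0.030") while the means place Mindfulness above CBT. The document does not rank those two arms, and IVRTS leads on both counts.
- *That dividing each HAM-A difference by its printed t gives intervals that overlap, so the IVRTS lead is doubtful.* Overlap of two comparisons with Control does not test one active arm against the other, and those t-values do not fit their own tables.

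**Conclusion.** The point holds in a limited form. The t, p and SD grounds do not support the ranking of IVRTS over CBT and Mindfulness, and the p below 0.01 claimed for those comparisons has no reported test. The one ground that can describe an ordering, the means, is given without an estimated difference, an interval or baseline adjustment. The ranking is not thereby shown to be false.

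On size, one criterion on one scale fails to put IVRTS first (HAM-A t, 8.088 against 8.350). The HAM-A advantage over Mindfulness could lie anywhere from 4.26 to 8.52 points, and over CBT from 6.01 to 9.93, if the baseline slope is between 0 and 1.

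The printed t-values are not a safe base for anything more precise. With the printed n they fit neither post-score tests nor change-score tests with a plausible correlation, and the printed p-values point to about 57 df instead of 229 to 241. A reader might infer that the tests were run on about 30 patients per arm. With 29 or 30 per arm, all nine t-values would fit change-score tests with r between 0.56 and 0.84. No passage states such an n, and only the patient data can settle it.

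**What to change.** 1. Check t, p and n in the three Control-comparison tables against the patient data, including the IVRTS QOL p. State whether each test uses post or change scores.
2. In the text on Table 4, remove t-scores, p-scores and SDs as grounds for ranking.
3. For each scale, fit one ANCOVA of post score over all four arms with the baseline score as covariate. Add to Table 4 the adjusted differences for IVRTS versus Mindfulness, IVRTS versus CBT and each arm versus Control, with 95% CIs.
4. Word the conclusion from those estimates. Either give the test behind the claimed p below 0.01 or withdraw that sentence, and align the ABSTRACT and DISCUSSION AND CONCLUSION.
5. Do not print intervals back-calculated from the published t-values.

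The cost is re-analysis of data already held, one extended table and some rewording. The downside for the sponsor is that adjustment for the lower IVRTS baseline on HAM-A may shrink the reported advantage.

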Figure 2: Intelligent Interactive Psychotherapy Program Software (IIPPS)

Objective

To develop Novel Technology, Intelligent Virtual Reality Therapy System (IVRTS) and test its Clinical Efficacy to treat phobias and anxiety, compared to Mindfulness Meditation and Cognitive Behavior Therapy (Talk Therapy).

Concept

Virtual Reality has a vast potential in healthcare. One such area where VR is becoming a promising technique is the treatment of Phobias and Anxiety Disorders. There are various types of phobias, and amongst them, some occur more commonly in individuals, in general. In the treatment of phobia using VR, the patient re-enters a computer-generated environment that is the imitation of the situation or an object the patient possesses the fear of. It helps people to encounter situations or objects they fear while being in a completely safe and controlled environment. The environment is

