The Inclusion criteria included patients visiting the Psychiatry OPD of University College of Medical Sciences of the University of Delhi and the attached GTB Hospital.

Furthermore, those patients were selected who reported fear of heights and scored mild, moderate and Severe anxiety as assessed on Hamilton Anxiety Inventory. The patients were in the age group between 18 to 60 years of age.

Exclusion Criteria

Patients who had any Psychotic disorder or symptoms co-morbid were not selected for the study. Furthermore, patients below 18 years of age and aver 60 years of age were also not selected for the program

Registration

All procedures involving human subjects/patients were jointly approved by The University College of Medical Sciences (University of Delhi) and Delhi Psychiatry Society Ethics Committee registration. Registration number 3/1/333011/HRD. The patients were first recruited on 5th February 2018 for the project.

Procedure and Approaches

To achieve the stated objective, a two-fold approach comprising of qualitative and quantitative analysis was undertaken. A 7-week intervention course was designed for each subject to reduce symptoms and enhance quality of life as well as to establish clinical efficacy. The intervention was conducted on a sample of 500 patients diagnosed with Acrophobia co-morbid with generalized anxiety who underwent the intervention at The GTB hospital of The University of Delhi, for a total of 3500 sessions, ranging up to 5250 Hours over a period of 2 years. Written informed consent was obtained from all participants. The authors assert that all procedures contributing to this work comply with the ethical standards of the relevant national and institutional committees on human experimentation and with the Helsinki Declaration of 1975, as revised in 2008. All procedures involving human subjects/patients were jointly approved by The University College of Medical Sciences (University of Delhi) and Delhi Psychiatry Society Ethics Committee registration. Registration number 3/1/333011/HRD. Further study carried out A-B-A research design which mainly involved establishing a baseline condition, introducing an experimental treatment and then returning to the baseline. The subjects

completed standardized self-report measures of Hamilton Anxiety Inventory (HAM-A),
Subjective Units of Dysfunction (SUDS) and WHO Quality of Life - BREF Questionnaire

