(QOL-BREF) at baseline, after seven intervention sessions post assessments on the same scales were repeated to assess the efficacy.

The Therapeutic Software of IVRTS

The researchers developed four different technological approaches to develop the Psychotherapeutic Software. (1) Since phobias are known to stem from mental images of situations or objects which an individual has learned to be fearful of. Thus, the most effective way to treat them, then, would be to alter these anxietyprovoking images with the help of graded exposure of an image of a situation or object which induces maximum pleasure and positive emotions within the individual. This was achieved with the help of development of motion sensors to detect the wrist movements of the subjects, which aided in achieving the desired goal of stimulating the pleasure-inducing stimulus to reduce anxiety. This was accompanied by monitoring the subject's physiological parameters through body biofeedback and fNIRS depicting the changes brought about by VR therapy and keeping the record of the same. (2) When an individual encountered a fearful stimulus, certain kind of neurotransmitters are released in the brain and over time, the body and mind of the individual learn to associate the release of these neurotransmitters with fear. This association was altered by flooding the individual's mind with pleasurable memories in the form of positive images using Virtual Reality Technology and thereby replacing unpleasant memories attached to the neurotransmitter release with pleasant memories. It was followed by guided instruction from the IVRTS device along the concept of 'Whole Brain Thinking' wherein all the five sense organs are used to exercise all the parts of the brain to take advantage of a wide spectrum of thinking. (3) As described in Figure 1, Cognitive Behavioral Therapy

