(CBT) states that it is not the situation itself but the thought associated with the situation (stimulus) which makes an individual fearful. Altering this thought and the emotions related to it is hence helpful in treating phobias. This was achieved by integrating an automated intelligent Cognitive Behavior Therapy software program with the VR device. 4) Finally, the researchers used Mindfulness Relaxation as a treatment for phobia. This was implemented by making the subject face the anxiety-provoking situation with the help of VR equipment and simultaneously working on reducing the anxiety emotions with the help of guided mindfulness meditation accompanied by meditation music, along with the developed automated intelligent therapy software interface. This methodology was intended to put the subject in a peaceful state of mind, detaching them from negative thoughts and fears, working on the principle that anxiety and relaxation cannot coexist.

[figure not shown]

Figure 6: Understanding CBT Software

Project Plan

[figure not shown]

Figure 7: Project plan

01/08/2020

OUTCOMES AND RESULTS

The quantitative and qualitative results were analyzed with the appropriate statistical and analytical tools. Various statistical modalities were used to establish efficacy, efficiency and the frequencies evaluated. Paired sample t- test were conducted in this study to assess the statistical significance of the interventions.

Independent sample t-test and ANOVA were tested in the data. Correlation analysis was also performed, The association between two categorical variables is enumerated by Chi-square test.

Scale	Mindfulness (n=118)		Control (n=125)		t-	F-	p-value
	Pre	Post	Pre	Post	value	value	
	Mean±SD		Mean±SD				
HAMA	32.86±5.76	19.62±4.24	33.70±6.08	28.00±6.49	8.350	2.327	0.000
SUDS	8.24±0.95	5.69±1.04	8.27±1.11	6.03±1.29	1.228	0.178	0.225
QOL	73.86±7.73	84.10±5.19	75.47±5.44	82.53±4.85	-2.229	6.242	0.030

Table 1: Mean comparison between Mindfulness Meditation group (n=118) and control group (n=125)

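### The results section calls IVRTS the most efficient intervention, but the visible text and tables define no efficiency measure and report no treatment time, therapist time or cost by arm

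*Combined protocol and SAP*

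**What the plan says.** All references are to the combined protocol and SAP.

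- **Outcomes and Results, opening paragraph.** "Various statistical modalities were used to establish efficacy, efficiency and the frequencies evaluated". Efficacy and efficiency appear as two separate items, and neither is defined there.
- **Outcomes and Results, paragraph after Table 4.** The comparison is presented as one "to show which intervention proved to be the most effective and efficient for the patients". The paragraph then concludes that the IVRTS "intervention is the most effective and efficient intervention compared to Mindfulness and even CBT". It gives its basis as "comparisons of statistical significance modalities namely, The Mean Scores, Standard Deviations, t-scores and p-scores".
- **Table 4**, on which that paragraph relies, is titled "Efficacy of Interventions based on the HAMA, SUDS and WHO QOL scale".
- **Procedure and Approaches.** The three scales are completed at baseline, and "after seven intervention sessions post assessments on the same scales were repeated to assess the efficacy". The only exposure figures are for the whole trial: "for a total of 3500 sessions, ranging up to 5250 Hours over a period of 2 years".
- **Objective.** The aim is to develop the technology and "test its Clinical Efficacy to treat phobias and anxiety, compared to Mindfulness Meditation and Cognitive Behavior Therapy". Neither the Objective nor the Hypothesis section names efficiency as something to be tested.
- **Rationale, Novelty of the Project, Concept and Relevance to Society.** These sections describe expected benefits: use without a therapist, lower cost, therapist time saved, and treatment time cut by about half.

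**The concern.** A claim that one treatment is more efficient than another normally compares what was gained with what was spent. The trial reports gains on three scales. It reports nothing by arm on what was spent, whether contact time, staffing or money. The conclusion therefore contains a comparative claim against CBT and Mindfulness that the stated evidence cannot bear on.

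This matters because the Introduction justifies new treatments partly by the shortage of clinicians, and other sections promise savings in therapist time, cost and duration. A reader with those needs could take the sentence as a tested finding that IVRTS uses fewer resources than CBT. The Limitations section does not say that this was left untested.

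**Working it through.** **Step 1. What the tables contain.** Tables 1 to 3 compare each active arm with control, and Table 4 sets the three active arms side by side. Every row in all four is HAM-A, SUDS or QOL. That is three scales and no measure of time, staffing or cost. The physiological recordings described elsewhere (blood pressure, heart rate, fNIRS) have no tabulated results and would not measure resource use.

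**Step 2. The pooled totals.** Inputs: 500 patients, seven sessions each, 3500 sessions and up to 5250 hours (Abstract; Procedure and Approaches).

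- Sessions: 500 × 7 = 3500, which reproduces the stated total.
- Hours per session: 5250 / 3500 = 1.5, on average and at most, since Procedure and Approaches gives the hours as an upper limit.
- Hours per patient: 5250 / 500 = 10.5, on the same basis.

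The session total fits one nominal seven-session course for everyone randomised, control arm included. One total over four arms cannot be split by arm without further data, so it shows no saving for IVRTS. The tables cover 118 + 106 + 115 + 125 = 464 patients, and 464 × 7 = 3248, so 3500 may be a planned rather than a delivered count. Neither figure can be divided by arm.

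**Step 3. Efficient as improvement per session.** Inputs: the pre and post means in Table 4. These are raw changes, used descriptively only.

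| Scale | IVRTS | CBT | Mindfulness |
|---|---|---|---|
| HAM-A fall | 28.60 − 11.10 = 17.50 | 32.52 − 21.03 = 11.49 | 32.86 − 19.62 = 13.24 |
| SUDS fall | 8.10 − 3.73 = 4.37 | 8.24 − 5.34 = 2.90 | 8.24 − 5.69 = 2.55 |
| QOL rise | 87.07 − 72.87 = 14.20 | 83.28 − 73.62 = 9.66 | 84.10 − 73.86 = 10.24 |

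Dividing the HAM-A falls by seven gives 2.50, 1.64 and 1.89 points per session. The ratios are:

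- IVRTS to CBT: 17.50 / 11.49 = 1.52, and (17.50 / 7) / (11.49 / 7) = 1.52.
- IVRTS to Mindfulness: 17.50 / 13.24 = 1.32, and again 1.32 per session.

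The divisor cancels, so the same holds for SUDS (1.51 and 1.71) and QOL (1.47 and 1.39). With a common nominal number of sessions, improvement per session carries no information beyond improvement.

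**Step 4. Efficient as a saving of resources.** This needs time, staffing or cost by arm. By steps 1 and 2 none is reported, so there is nothing to compute.

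**The case against.** The strongest reply is that the authors use the word loosely. Every comparison in the paragraph after Table 4 is a scale score, the first use refers to what works for the patients, and no saving is reported there as a result. With equal input, more improvement per session is an ordinary meaning of efficient, and Table 4 does hold data on that. This part stands: it would be wrong to say that no data of any kind lie behind the word. On that reading, though, the word is redundant, as step 3 shows. The opening paragraph of the section also lists efficacy and efficiency separately, which weighs against treating them as synonyms.

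A second reply is that the savings are plainly worded as expectations. This largely stands. Most of those statements are conditional; the Concept section is firmer but describes what the system is meant to do. A reader might infer that the documents present lower cost, shorter treatment or therapist-free use as trial results, but the wording does not support that, and those sections need no relabelling.

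A third reply is that the Abstract's conclusion and the Discussion claim only greater effectiveness. This is correct. A reader might infer that half of the study's conclusion is without support, but that overstates what is one adjective in two results sentences and one noun in a methods sentence.

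Finally, several figures are not shown, and a qualitative analysis is mentioned without visible results. The finding is therefore limited to the visible text and tables. The basis stated for the conclusion is quantitative, so this gap is unlikely to matter.

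**Conclusion.** The point holds as a minor correction to a stated conclusion. Three sentences in Outcomes and Results are affected. Read as improvement per session, the efficiency claim repeats the effectiveness claim; read as a saving of resources, it was not tested. No estimate, test or table entry changes.

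A reader might infer that IVRTS has been shown not to save time or money. The documents do not support that either: the pooled totals fit equal nominal exposure but say nothing about actual use in each arm, so the question is open. Nor does this point say anything for or against the effectiveness claim, which has to be judged separately.

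The verdict assumes that the seven-session course applied nominally to every arm, as Procedure and Approaches implies and 500 × 7 = 3500 supports, and that the figures not shown contain no resource data by arm.

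**What to change.** 1. In the paragraph after Table 4, delete *and efficient* from both sentences in which it appears.
2. In the opening paragraph of Outcomes and Results, delete *efficiency* from the list of what the statistics were used to establish.
3. Add to Limitations, Challenges and Future Scope: *Treatment time, therapist time and cost were not compared between arms; therapist-free use, lower cost and a treatment time reduced by about half were not tested in this trial.*

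These are text edits that need no new data or analysis. The cost is the loss of the efficiency claim. The edits also bring the results section into line with the Abstract's conclusion and the Discussion. A post hoc comparison of therapist time is not needed for this correction.
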